### **• Background of research and expected project commencement date**

Emerging infections have been shown to have an important impact on pregnant women and their fetuses. Recent examples include the 2009 pandemic H1N1 influenza virus and the Zika virus. The emergence of a novel coronavirus not previously seen in humans, namely severe acute respiratory syndrome coronavirus 2 (SARS-CoV-2), was first reported in Wuhan, China, on December 31, 2019. The coronavirus disease 2019 (COVID-19), caused by the SARS-CoV-2, was declared by the World Health Organization (WHO) a pandemic on 11 March 2020. Since then, the number of reported cases has increased rapidly, with more than 10 million cases and 500000 deaths as of 1 July, 2020.

Coronaviruses are single-stranded RNA, non-segmented, enveloped viruses, which cause illness ranging in severity from a common cold to severe and fatal illness. The term coronavirus derives from the Latin word corona, which means crown or halo; the designation arises from the appearance of coronavirus virions viewed by electron microscopy (EM), in which the virus particles display a crown-like fringe typically referred to as spikes. In the past 2 decades, two notable coronaviruses, severe acute respiratory syndrome coronavirus (SARS-CoV) and the Middle East respiratory syndrome coronavirus (MERS-CoV), have caused severe respiratory illness in humans. Within a short period of time, the third coronavirus, SARS-CoV-2, has infected far more people than were reported for MERS-CoV and SARS-CoV combined.

It is recognized that pregnant women are at an increased risk of acquiring viral respiratory infection and developing severe pneumonia due to the physiologic changes in their immune and cardiopulmonary systems. It is important to determine the effect of the SARS-CoV-2 infection

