#### **Objective 5: Potential mechanisms for vertical transmission**

Currently there is much controversy regarding the possibility of vertical transmission of SARS-CoV-2 infection. There is a need for a systematic approach to characterize the transmission potential of SARS-CoV-2. In order to successfully establish an infection and transmission of the virus in the target tissues, i.e. placenta and developing fetus, SARS-CoV-2 has to be able to dock and invade the placental barrier as well as to overcome the host immunologic response at the site of infection. In order to have a comprehensive investigation of these underlying mechanisms, laboratory tests will be divided into 3 parts to evaluate: 1) placental barrier, 2) immune response and 3) fetal damage of vertical transmission and mechanism in SARS-CoV-2 infection.

Methodology: For the placenta collected from pregnant women affected by COVID-19 (objective 4), dissect it into 10 full-thickness samples (1 x 1 cm) from 10 random sampling sites, away from cord insertion site and far apart from each other. Three of these samples will be stored in 10% buffer-formalin and 2 of them will be stored in EM fixative. For the remaining 5 samples, they will be dissected into 3 parts: chorionic plate, villous and maternal decidua; and store these samples into separate micro-tubes that will be frozen by snap freezing in liquid nitrogen or dry ice and subsequently stored at -80°C.

Placental barrier: we will look into localization, infection, replication and resistance of the viral infection in decidua, amnion, maternal-fetal interface, syncytium and placenta. Tissues and cells from COVID-19 affected pregnancies with live birth (objective 4) and pregnancy loss (objective 2) will be collected and isolated for the study; unaffected pregnancies with live birth and pregnancy loss will also be recruited as control for comparison. Standard scanning EM (SEM) and transmission EM (TEM) will be employed. SEM could provide detailed images of the surfaces of cells, so that the distribution and site of infection of the virion in the maternal, interface and fetal compartments could be located. While TEM provides details of interior structures within the cell, and thus any dysplasia or reconfiguration of cellular organelles due to viral infection could be studied.

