Immune response: during viral infection, the virus has to employ host cell surface molecules as specific adhesive receptor. This interaction between the virus and the host cells induces conformational changes on both the viral protein as well as the host plasma membrane, and in turns, promotes viral entry. Viral entry could generally fall into two categories: 1) direct infection of the placenta or 2) indirect infection via transcytosis. Whether SARS-CoV-2 employs direct infection and/or indirect infection through virion transcytosis syncytium will be determined. Results will also correlate with the viral +sense ssRNA load and histologic changes in the corresponding cells. Meanwhile, it has been confirmed that the SARS-CoV-2 invades human cells by utilizing two protein molecules: receptor of angiotensin-converting enzyme 2 (ACE2) which aids in host cell attachment, and a transmembrane serine protease (TPRSS2) which further assists cell entry. The relative abundance, distribution and co-localization of these cell surface proteins in different epithelial, stroma, endothelial, trophoblast, fibroblast and various immune cells will be measured and compared between COVID-19 cases and controls. Efficiency and resistance infection will be measured by viral replication in various human trophoblast primary cells and tissue explants using viral-specific neutralizing antibody titers. Tissue-specific spread, cell-to-cell spread, and bypass of the viral infection will be determined. Nonetheless, not all cells displaying these required receptors are permissive to productive infection. The presence or absence of specific host proteins may also play a critical role during viral infection. Little is known about how these intracellular host factors may influence successful SARS-CoV-2 infection. In order to address this question, we will look into the immunologic reaction of the cells in the decidua, amnion, maternal-fetal interface, syncytium, placental villi core and maternal and cord/fetal blood. Single cell RNA sequencing (scRNAseq) of maternal-fetal interface, maternal blood and cord blood will be conducted in the affected pregnancies with live birth and pregnancy loss. Gene expression of viral infection cascades (e.g. HLA-G, FcRn, TLR, NOD, defensin, etc) and surface molecules (e.g. ICAM, Cadherin, gap junction, etc) in epithelial, stroma, endothelial, trophoblast, fibroblast and various immune cells will be measured and compared with controls. Cell-specific mechanism of immune evasion and defense of SARS-CoV-2 infection for vertical transmission will be determined.

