
For fetal damage, we will look into the fetal barrier and immune response of the viral infection in the affected fetuses. POC and stillborn babies of affected pregnancies will be collected and isolated for SEM and TEM, ssRNA load qualification, and viral replication to confirm the localization, infection, replication and immunologic reaction as above. If the fetuses have any developmental structural abnormalities identified during antenatal ultrasound examinations, the affected fetal organs, tissues and cells will be specifically collected and studied as above. The results will be correlated with the pathology of the fetuses and compared with the POC and stillborn fetuses of unaffected pregnancies.

Target achievement: We aim to collect 5-10 affected cases with live birth and 5-10 affected cases with pregnancy loss, compared with gestational-age matched controls. We anticipate to characterize and reveal underlying mechanisms for vertical transmission associated with pregnancy loss and fetal complications.

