### SARS-CoV-2 target cells

Together with [name], we have conducted a pilot study and applied bioinformatic analysis on published scRNASeq datasets of early trophoblastoderm (TE) and first and second trimester placentas and identified the existence of ACE2 and TMPRSS2 expression in human TE and first and second trimester placentas (Figure 1). In human TE data, 54.4% of TE cells, 9.0% of cytotrophoblasts (CTBs), 3.2% of extravillous trophoblasts (EVTs) and 29.5% of syncytiotrophoblasts (STBs) were ACE2 positive. As for TMPRSS2, 90.7% of TE cells, 31.5% of CTBs, 22.1% of EVT and 70.8% of STBs were TMPRSS2 positive. Amongst the placental cells, 20.4% of CTBs, 44.1% of STBs, 3.4% of EVT at 8 weeks and 63% of EVT at 24 weeks were ACE2 positive. And 1.6% of CTBs, 26.5% of STBs, 1.9% of EVT at 8 weeks and 20.1% of EVT at 24 weeks were TMPRSS2 positive. Pathway analysis revealed associations to morphogenesis of branching structure, extracellular matrix interaction, oxygen binding and antioxidant activity in ACE2+TMPRSS2+ EVT at 24 weeks cells. The ACE2+TMPRSS2+ TE cells were correlated with an increased capacity of viral invasion, epithelial cell proliferation and cell adhesion. Based on immunohistochemical results, a higher expression level of ACE2 and TMPRSS2 in first and second trimester placentas was observed (Figure 2). Localization of virion in the maternal, interface and fetal compartments; and associated dysplasia or reconfiguration of cellular organelles will be examined by TEM as we have previously described.

**Table 1.** Biological samples from cases of pregnancy loss

Biological samples	Tests to be done
Miscarriage POC *∞ , maternal blood #	*SARS-CoV-2 RT-PCR; # IgG; ∞ HPE;
Stillbirth Maternal vaginal swab †¶ , amniotic fluid †¶ , amnion-chorion interface swab †¶ , placental tissue ¶ , fetal blood ¶‡ , fetal throat swab †¶ , maternal blood ‡	† Culture+PCR; ¶ SARS-CoV-2 RT-PCR; ‡ IgG

[figure not shown]
**Table 2.** Biological samples from pregnant cases affected by COVID-19

Biological samples	Tests to be done
Before delivery: maternal blood *#	*RT-PCR; # IgG and IgM;
At or after delivery: amniotic fluid*, cord blood*, placental tissue*, amnion-chorion interface swab*, neonatal throat swab*	† HPE

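### Objective 5 names neutralizing antibody titers as the readout for viral replication in trophoblast cells and explants, but such titers do not measure replication

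*Protocol*

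**What the plan says.** All the relevant text is in the protocol, almost all of it under Objective 5.

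- **Aim.** The Immune response part undertakes to settle the route of entry: "Whether SARS-CoV-2 employs direct infection and/or indirect infection through virion transcytosis syncytium will be determined". It also warns that carrying the entry receptors does not by itself make a cell permissive to productive infection.
- **Replication readout.** The same part says: "Efficiency and resistance infection will be measured by viral replication in various human trophoblast primary cells and tissue explants using viral-specific neutralizing antibody titers".
- **RNA load.** "Results will also correlate with the viral +sense ssRNA load and histologic changes in the corresponding cells".
- **Electron microscopy.** The Placental barrier part plans scanning EM so that "the distribution and site of infection of the virion in the maternal, interface and fetal compartments could be located", and transmission EM so that "any dysplasia or reconfiguration of cellular organelles due to viral infection could be studied". The section on SARS-CoV-2 target cells repeats the second purpose: "associated dysplasia or reconfiguration of cellular organelles will be examined by TEM".
- **Fetal tissue.** The fetal damage part lists SEM and TEM, then "ssRNA load qualification, and viral replication to confirm the localization, infection, replication and immunologic reaction as above".
- **Size.** The target is 5-10 affected live births and 5-10 affected losses, with controls matched on gestational age.

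**The concern.** The protocol distinguishes a cell that virus can enter from a cell in which virus multiplies, and it promises to measure the latter. The tool it names belongs to a different question. A neutralizing titer is a property of an antibody-containing sample, usually serum. Trophoblast cultures and explants do not make that antibody, so the titer has no reason to rise when virus multiplies in them.

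At stake is the permissiveness result. If the sentence is followed literally, permissive and resistant cultures could return the same titer, and the study would have no measured basis for statements about efficiency of, or resistance to, infection. Affected cases are few, so the readout should be settled before tissue is used.

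**Working it through.** The protocol gives no figure to reproduce here. The check sets each planned readout against the question it has to answer.

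**Step 1: neutralizing titer against replication.** The titer records how far an antibody sample can be diluted and still block infection. Take two cultures given the same virus, one permissive and one resistant. Virus output differs between them. The titer depends on the antibody sample and not on the cells' output, so it need not differ. The readout does not match its endpoint.

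**Step 2: +sense RNA load against replication.** The Background section says: "Coronaviruses are single-stranded RNA, non-segmented, enveloped viruses". The Immune response part calls the measured RNA +sense. The strand being measured is therefore the genome that a virion carries. Write the load in a tissue sample as

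L = C + R,

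where C is RNA in virions that were carried, trapped or blood-borne, and R is RNA newly made by the cells. One measurement of L at one time cannot identify R: the same L fits R = 0 with a large C, or a large R with a small C. Repeated measurement in an inoculated culture is different. After inoculation no further virus is supplied from outside, so C does not grow and a rise in L reflects R. A time course can therefore serve as a replication readout where a single tissue load cannot.

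**Step 3: the remaining readouts.**

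- Scanning EM locates virions by compartment. Transmission EM shows structure and organelle change inside the cell. Both bear on route of entry. Neither quantifies replication efficiency.
- Histology shows tissue change. It bears on infection but does not measure viral output.
- Single-cell RNA sequencing is described for host gene expression, not viral replication.

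**Step 4: search for any other replication assay.** Objective 5 and the target-cell section name no negative-strand or subgenomic RNA target, no infectious-virus titration and no time course of viral yield.

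**Step 5: fetal tissue.** RNA load and viral replication appear there as separate items, so RNA load is not offered as the replication measure. The closing words refer back to the earlier parts, where the only replication method is the antibody titer. The reference may attach to the method, or only to the list of features to be confirmed. The text does not settle which.

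**Result.** For replication, one readout is named and it does not measure replication. For direct infection versus transcytosis, the usable evidence is EM and histology.

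**The case against.** The strongest reply is that the sentence is loosely worded rather than wrongly planned. Its stated measurand is viral replication, and the antibody phrase may be shorthand for infecting cells and explants with a neutralization step. That is possible. But a neutralization assay still reports antibody potency, so the charitable reading does not supply a replication measure, and the protocol fixes this readout in words rather than leaving it open.

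Three stronger readings are tempting, and the protocol does not support them.

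- A reader might infer that the plan diagnoses infection from +sense RNA load. It does not. Results are to be correlated with that load and with histologic changes, and no passage defines infection by it.
- A reader might infer that direct infection could never be told from passive carriage. That goes too far. SEM, TEM and histology are planned, and virions or organelle change inside cells bear on that question. The protocol states no criterion for productive infection on EM, but that could sit in a laboratory manual and is not counted here as a defect.
- A reader might infer that all Objective 5 results fail. The antibody sentence covers primary cells and explants only. The EM, RNA-load, receptor and sequencing work on case tissue does not depend on it. Objective 4 judges vertical transmission by RT-PCR and/or antibody testing and is untouched.

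It is also fair to say that this is a small mechanistic aim with no stated hypothesis test. That limits the weight of the point but does not remove it.

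**Conclusion.** The point stands in a limited form. The one readout named for viral replication in trophoblast cells and explants measures antibody potency, so it could not separate permissive from resistant cells. The +sense RNA load does not make up for this. The route-of-entry question would rest on EM and histology, which are relevant but do not quantify replication.

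The size is qualitative: one stated laboratory endpoint is not measured as written. Carry-over to fetal tissue is uncertain because of the ambiguous back-reference. Sample size, power, error rates and patient handling are unaffected. The protocol should be corrected, but the rest of Objective 5 is not undermined.

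The conclusion assumes the ordinary meaning of a neutralizing titer, and that the +sense RNA named in the protocol is the viral genome, as its own description of the virus implies.

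**What to change.** 1. **Immune response, cells and explants.** Replace the neutralizing-titer readout with a replication readout in the same planned cultures: infectious-virus yield, or cell-associated viral RNA, measured over time after inoculation.
2. **Neutralizing titers.** If they are wanted, keep them only as a measure of the maternal and cord serum response.
3. **Fetal damage.** State that the viral replication item and its back-reference do not mean neutralizing titers. Where stored frozen tissue allows, add a replication-specific RNA target (negative-strand or subgenomic) beside the +sense load.
4. **Interpretation.** Read that target together with EM and histology. It should not become the sole rule for calling a tissue infected, which would be a debatable choice in its own right.

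**Cost.** Some additional laboratory work on planned cultures and stored tissue. Frozen material is foreseen: Objective 5 takes 10 placental samples, of which 10 - 3 - 2 = 5 are snap-frozen after the formalin and EM samples are set aside, and Objective 2 also freezes products of conception, placental and fetal tissue. The protocol does not say that RNA has already been extracted, nor does it describe the inoculation or titration set-up, so the laboratory should confirm feasibility before choosing between the two culture readouts. No additional participants are needed.

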## **Project objectives**

- 1) To determine the rate of SARS-CoV-2 seroconversion in unselected pregnant women in Hong Kong.
- 2) To determine the rate of SARS-CoV-2 infection in women presenting with miscarriage and stillbirth.
- 3) To follow the pregnancy course and perinatal outcome of confirmed COVID-19-infected pregnant cases.
- 4) To determine the risk and characteristics of vertical transmission.
- 5) To evaluate the placental barrier, immune response and fetal damage in vertical transmission of SARS-CoV-2.

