separate micro-tubes that will be frozen by snap freezing in liquid nitrogen or dry ice and subsequently stored at -80°C. Abortus/stillborn baby will be washed in cold saline or PBS to remove blood. Dissect the abortus/stillborn baby into different body parts, e.g. lungs, cartilage, skull, brain, muscle, intestines, and store them into separate micro-tubes that will be frozen by snap freezing in liquid nitrogen or dry ice and subsequently stored at -80°C. Stillborn baby will also undergo routine autopsy and histopathological examination (HPE) of placenta. All placentas will be photographed against a scale bar. In addition, hematoxylin-eosin, myeloperoxidase immunohistochemistry, Gram, and periodic acid-Schiff colorations will be performed on POC and placenta that are tested positive for SARS-CoV-2 to exclude coexisting bacterial infection. Results on the rate of SARS-CoV-2 infection in women with pregnancy loss will be summarized in counts and percentages. Target achievement: we aim to recruit 500 and 5 pregnant women with miscarriage and stillbirth, respectively, to determine the rate of SARS-CoV-2 infection in women presenting with early and late pregnancy loss, and in cases with positive SARS-CoV-2, matched with negative cases, whether vertical transmission has contributed to these complications (see details in objective 5).

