In our high-quality systematic review, we have summarized data on clinical characteristics, including at least one maternal, perinatal or neonatal outcome, in 295 pregnant women affected by COVID-19 from 8 consecutive case series. Amongst these 295 cases, 210 cases originated from China. We have also identified a high number of possible duplicate reporting and excluded 327 cases from China. The most common symptoms at presentation were fever, cough, dyspnea/shortness of breath, fatigue and myalgia. The rate of severe pneumonia reported amongst the case series ranged from 0 to 14%. Almost all cases from the case series had positive computer tomography chest findings. Only 4 cases of spontaneous miscarriage or abortion were reported. In the consecutive case series, 219/295 women had delivered at the time of reporting, and of these, 78.1% had Cesarean section. The gestational age at delivery ranged from 28 to 41 weeks. Apgar scores at 1 and 5 min ranged from 7 to 10 and 7 to 10, respectively. Only eight (8/103; 7.8%) neonates had birth weight <2500 g and nearly one-third of cases (49/173; 28.3%) were transferred to the NICU. There was one case each of neonatal asphyxia and neonatal death. In 155 neonates that had nucleic-acid testing in throat swab, all, except three cases, were negative for SARS-CoV-2. Our systematic review has highlighted that despite the increasing number of published studies on COVID-19 in pregnancy, there are insufficient good-quality data to draw unbiased conclusions with regard to complications of COVID-19 in pregnant women as well as vertical transmission and perinatal complications. Our research to date will form the basis of our prospective studies described in this proposal. In addition, the PC is a project partner for a UK Research Institute (UKRI) and NIHR funded international registry of pregnancy and neonatal outcomes of COVID-19 (PAN-COVID; <https://pan-covid.org>). This registry is an international observational study with a web-based portal, collecting data on outcomes of pregnant women and their newborn babies who have suspected COVID-19 in pregnancy or confirmed SARS-CoV-2 infection. The registry will focus on reporting the incidence of the following outcomes: miscarriage, FGR and stillbirth, preterm delivery, vertical transmission and early-onset neonatal

SARS-CoV-2 infection. Data from our proposed project will have the opportunity to be compared with data collected through PAN-COVID.

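### Objective 5 names no comparison of infected pregnancies with and without transmission, so its case-control differences describe effects of maternal infection and cannot by themselves identify factors tied to vertical transmission

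*Protocol*

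**What the plan says.** The protocol's Project objectives give the aim as "To evaluate the placental barrier, immune response and fetal damage in vertical transmission of SARS-CoV-2". The Target achievement paragraph of Objective 5 sets the case groups, "We aim to collect 5-10 affected cases with live birth and 5-10 affected cases with pregnancy loss, compared with gestational-age matched controls", and the intended conclusion, "We anticipate to characterize and reveal underlying mechanisms for vertical transmission".

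The comparators are described in four places:

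- Objective 5, placental barrier: "unaffected pregnancies with live birth and pregnancy loss will also be recruited as control for comparison".
- Objective 5, immune response: ACE2 and TMPRSS2 abundance, distribution and co-localization "will be measured and compared between COVID-19 cases and controls". Gene expression is likewise compared with controls.
- Objective 5, fetal damage: results are "compared with the POC and stillborn fetuses of unaffected pregnancies".
- Objective 2 asks, "in cases with positive SARS-CoV-2, matched with negative cases, whether vertical transmission has contributed to these complications (see details in objective 5", and so refers its own question to Objective 5.

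Objective 5 also plans work that does not rest on these contrasts: locating virions by electron microscopy in the maternal, interface and fetal compartments; asking whether entry is direct or by transcytosis; correlating results with viral RNA load and histology; and measuring viral replication in trophoblast primary cells and explants.

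Objective 4 tests mothers and newborns to judge whether transmission occurred. Objective 5 takes its live-birth placentas from Objective 4, but does not say that the Objective 4 result is used to choose or group them.

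**The concern.** The groups are defined by whether the mother was infected, while the promised conclusion is about whether and how virus reached the fetus. Infected pregnancies with and without transmission are pooled as affected. A difference from unaffected controls may then reflect maternal illness, inflammation or treatment. Receptor and gene-expression levels are also measured after infection, so a difference may be a consequence of disease. If few or none of the affected cases involve transmission, a non-specific effect of maternal COVID-19 on the placenta could be reported as a transmission mechanism. Later analysis cannot fully repair this, because case selection decides which tissue is assayed.

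**Working it through.** **1. The named comparisons, side by side**

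| Component | Groups compared | Grouped by transmission? |
|---|---|---|
| Placental barrier tissue | Affected vs unaffected | No |
| ACE2/TMPRSS2 | COVID-19 cases vs controls | No |
| Gene expression | Affected vs controls | No |
| Fetal tissue | Affected vs unaffected POC and stillborn fetuses | No |
| Losses (from Objective 2) | SARS-CoV-2 positive vs negative | Not stated |

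In the last row the protocol does not say whether positive refers to the mother or to the products of conception (POC). On neither reading does it name infected mothers with virus-negative tissue as the comparator. Cases are stratified by live birth or loss only.

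**2. What the affected-unaffected contrast estimates**

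Let U, N and T be the mean of a measurement in unaffected pregnancies, infected pregnancies without transmission, and infected pregnancies with transmission. Let p be the share of affected pregnancies with transmission.

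- Affected mean = p·T + (1 − p)·N.
- Contrast = affected mean − U = (N − U) + p·(T − N).

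The quantity tied to transmission, T − N, enters with weight p and cannot be separated from N − U. At p = 0.019 it carries about 2% weight, and the contrast can be large when T − N is zero.

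**3. How many transmissions the cases might contain**

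The protocol gives no derivation for 5-10 cases per group, so there is no figure to reproduce. Inputs:

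- "In 155 neonates that had nucleic-acid testing in throat swab, all, except three cases, were negative for SARS-CoV-2" (Pregnancy outcome and vertical transmission): p = 3/155 = 0.0194, exact (Clopper-Pearson) 95% CI 0.0040 to 0.0555.
- The 116-case series in the same section: 0 of 85 neonates positive, exact upper limit 4.2%.
- Objective 5: 5-10 affected live births. Objective 3: 40-50 affected pregnancies.

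Formulas, taking cases as independent with a common p: expected number = n·p; P(at least one) = 1 − (1 − p)^n.

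| n | Expected at 1.9% | P(≥1) at 1.9% | P(≥1) at 0.4% | P(≥1) at 5.6% |
|---|---|---|---|---|
| 5 | 0.10 | 9.3% | 2.0% | 24.8% |
| 10 | 0.19 | 17.8% | 3.9% | 43.5% |
| 40 | 0.77 | 54.2% | 14.8% | 89.8% |
| 50 | 0.97 | 62.4% | 18.2% | 94.3% |

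Example: 1 − (1 − 0.0194)^10 = 0.178. If only 25 women gave tissue (an assumption; the protocol gives no such number), the chance at 1.9% would be 38.7%.

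P(at least two) at 1.9% is 18.1% for n = 40 and 25.2% for n = 50. Expecting five transmissions would take 5/0.0194, or about 258 infected pregnancies.

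Because the proxy is rough, assumed rates of 5% and 10% give a range. P(at least one) in 5-10 live births is then 23-40% and 41-65%. P(at least two) in 40-50 pregnancies is 60-72% and 92-97%.

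**The case against.** A reader might infer that Objective 5 does nothing but compare infected with uninfected mothers, and so can say nothing about how virus crosses the placenta. The protocol does not support that. Virion localization by compartment, the entry-route question, correlation with RNA load, and replication in primary cells and explants all bear on mechanism without a transmitting group. What they do not do is explain why transmission differs between infected pregnancies, and they do not change what the receptor, gene-expression and fetal-tissue contrasts estimate.

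A reader might also infer that cases are picked without regard to Objective 4. The protocol is silent on how the 5-10 are picked, and silence does not show that.

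Other points on the plan's side:

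- **The rate is a proxy.** The 3/155 figure is throat-swab positivity. It may include infection after birth and does not cover placental infection or losses; the protocol gives no rate for either. The background section adds that most reports concern third-trimester infection. This stands, and the probabilities are indicative only.
- **The 40-50 may overstate available tissue.** Study coordination describes the China contribution as outcome data from an existing cohort. This stands, so 54-62% is a ceiling at that rate.
- **A contrast within affected cases would be tiny.** At 1.9%, 40-50 pregnancies give 0.77-0.97 expected transmissions, and measurement would still follow infection. This stands, so the comparison can only be descriptive.
- **Grouping could be left to an analysis plan.** That is partly true of reporting. The comparators, strata, target numbers and conclusion, however, are fixed in this protocol.
- **The objective is small and exploratory, and unaffected controls are a legitimate reference.** Both are true. The controls should stay, and the mismatch is with the conclusion promised.

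**Conclusion.** The point holds in limited form. All group comparisons named for Objective 5 are by maternal infection status, and none is by evidence of transmission within infected pregnancies. Those contrasts cannot by themselves support the conclusion promised in Target achievement. The rest of the laboratory work can inform mechanism, but not why some infected pregnancies transmit and others do not.

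On the throat-swab proxy, the chance that 5-10 affected live births include even one transmission is 9-18% (2-44% over the confidence interval). Choosing from all 40-50 affected pregnancies raises it to at most 54-62% (15-94%), and to less if not all give tissue. These figures assume independent cases, a common rate, and swab positivity standing in for transmission. The mismatch between comparator and conclusion does not depend on them.

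**What to change.** 1. **Case selection.** Choose the 5-10 live-birth cases for the stored-tissue assays after the birth-sample RT-PCR and IgM/IgG results of Objective 4. Take first any mother-infant pair with placental, cord or newborn evidence of infection, then affected pairs without it. Do not wait for the 6-18 month serology. Fresh primary-cell and explant work need not wait either.
2. **Reporting.** Describe affected cases by evidence versus no evidence of transmission. In losses, this means POC RT-PCR positive versus mother positive with POC negative. Keep unaffected controls as the reference for the effect of maternal illness.
3. **Conclusion.** State in Target achievement of Objective 5 that, if no or too few transmitting cases are found, case-control differences will be reported as effects of maternal infection on the placenta and not as mechanisms of vertical transmission. Given the numbers above, this is the indispensable part.

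Cost: protocol wording and the order of the assays. No extra patients are needed, and Objective 5 already provides for fixing and freezing placental samples at -80°C. The downside is that assays on stored tissue start somewhat later, and the comparison within affected cases will rest on very few cases.
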